### **COVID-19 related measures**

Considerations related to COVID-19 and related measures will be documented in a separate risk assessment and mitigation plan. Details relating to statistical analyses, handling of protocol deviations, handling of missing data, and any other considerations related to COVID-19 and related measures will be detailed in the Statistical Analysis Plan (SAP).

### **7.3 End of Study**

A subject will have fulfilled the requirements for study completion if/when the subject has completed all study periods, including the last scheduled follow-up visit as indicated in the Schedule of Assessments ([Table 1](#)).

The end of the study will be the last subject's last visit.

## 8 SELECTION OF STUDY POPULATION

Section 7.1 provides information regarding number of subjects planned to be randomized.

### 8.1 Inclusion Criteria

Individuals must meet all of the following criteria to be included in the study:

1. Subject has been diagnosed with AIS.
2. Subject or if applicable subject's legally acceptable representative (LAR)/ legally designated representative (LDR) consents to participation by signing the informed consent form (ICF) after receiving full information about the study.
3. Subject [REDACTED] is aged 18 to 90 years (inclusive) [REDACTED]  
[REDACTED] is aged 18 to 80 years (inclusive) at the time of Screening (Visit 1).
4. Subject has an NIHSS of 4 to 25.
5. Subject [REDACTED] is able to receive the 1st IP within 24 hours after stroke symptoms onset.  
[REDACTED]  
[REDACTED]
6. Subjects who are women of childbearing potential (WOCBP), or men whose sexual partners are WOCBP are able and willing to use at least 1 highly effective method of contraception during the study until 3 months after the last dosing of IP administration. A woman is considered to be a WOCBP after menarche and until she is in a postmenopausal state for 12 months or otherwise permanently sterile (for which acceptable methods include hysterectomy, bilateral salpingectomy, and bilateral oophorectomy). For the definition and list of highly effective methods of contraception, see [Appendix 1](#).

#### Neuroimaging Inclusion Criteria:

1. Subject has adequate renal function, has no history of severe allergic reactions to contrast agents, and is able to undergo a contrast brain perfusion with either MRI or computed tomography (CT).

2. [REDACTED] the subsequent subjects must adhere to the following Mismatch Profile on MRI (perfusion is included) or CTP [REDACTED]

\*\*

\*\* The mismatch ratio is determined in real time by site routine practice (e.g., RAPID or similar software, or other similar analyses) based on the difference between the ischemic core lesion volume and the Tmax  $\geq 6$ s lesion volume. If both a multimodal MRI and CTP are performed before enrollment, the later of the 2 scans is assessed to determine eligibility.

## 8.2 Exclusion Criteria

Individuals meeting any of the following criteria at Screening (Visit 1) or Baseline are ineligible to participate in this study:

1. During the current AIS episode, the subject has received or is scheduled to receive EVT and/or IV thrombolytic (e.g., rtPA) treatment based on the investigator's assessment of its potential benefit.
2. Subject has a pre-stroke disability (mRS >2).
3. Subject has Alberta Stroke Program Early CT Score of  $\leq 5$ .
4. Subject has symptoms of suspected subarachnoid hemorrhage, even if CT is normal.
5. Subject has imaging evidence of acute intracranial hemorrhage, intracranial tumor (except meningioma without parenchymal mass effect), arteriovenous malformations, other central nervous system lesions that could increase the risk of bleeding, or aneurysm requiring treatment.
6. Subject has significant mass effect with midline shift.
7. Subject has pre-existing medical, neurological, or psychiatric disease that would confound the neurological or functional evaluations, e.g., seizures at onset of the current AIS, dementia.
8. Subject has current uncontrolled hypertension despite treatment: systolic blood pressure  $>185$  mmHg or diastolic blood pressure  $>110$  mmHg before dosing at Screening (Visit 1).
9. Subject has hemorrhagic diathesis, coagulation factor deficiency or recent oral anticoagulant therapy with International Normalized Ratio (INR)  $>1.7$  or aPTT  $>1.5$  times of upper limit of normal range at Screening (Visit 1).
10. Subject has received conventional heparin within 48 hours before the 1st IP administration, except for low dose subcutaneous conventional heparin or low molecular weight heparin at a preventive dose.
11. Subject has received one of the new oral anticoagulants within 48 hours before the 1st IP administration, e.g., dabigatran, apixaban, rivaroxaban, and edoxaban, except for dabigatran-treated subject who has been given a reversal agent, idarucizumab, before the 1st IP administration.
12. Subject has platelet count  $<100,000/\text{mm}^3$  at Screening (Visit 1).
13. Subject has blood glucose concentration  $<50$  mg/dL or  $>400$  mg/dL at Screening (Visit 1).

14. Subject has moderate or severe hepatic, renal, and/or active infectious disease at Screening (Visit 1) as judged by the investigator. Subject with confirmed COVID-19 or influenza infection can be enrolled at the investigator's discretion.
15. Subject is lactating, pregnant (pregnancy test required for all female subjects of childbearing potential), or planning to become pregnant during the study.
16. Subject has had history of sICH, prior AIS, myocardial infarction, or serious head trauma within 90 days before Screening (Visit 1).
17. Subject has had any major surgery within 90 days before Screening (Visit 1), e.g., intracranial or intraspinal surgery, coronary artery bypass graft, obstetrical delivery, organ biopsy.
18. Subject has had a bleeding event within 21 days before Screening (Visit 1), e.g., gastrointestinal hemorrhage.
19. Subject has puncture of noncompressible vessels within 7 days before Screening (Visit 1).
20. Subject has a history of severe allergic reactions to LT3001 or excipients.
21. Subject has participated in another investigational study and received IP within 30 days before Screening (Visit 1) or 5 half-lives (whichever is longer).
22. In the opinion of the Investigator, the subject has serious, advanced, or terminal illness that will prevent improvement or follow-up visits.
23. In the opinion of the Investigator, the subject is not appropriate for the study for any other reason.

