## 5.2 Background on LT3001

LT3001 [REDACTED] is a novel small molecule designed to have both thrombolytic and free radical scavenging activities, which were characterized in various *in vitro* and *in vivo* models. *In vitro* studies have shown that LT3001 exhibits substantial anti-oxidation activity. In animal studies, LT3001 can restore blood flow, reduce cerebral infarct volume, and improve neurological outcome in rodent and non-human primate stroke models, with an apparent wider therapeutic time window and a better safety profile than those reported for rtPA. Effect of LT3001 on the bleeding time was evaluated in male Institute of Cancer Research mice using an amputation tail model. The tail bleeding time of mice treated with [REDACTED] LT3001 was comparable to animals that received vehicle control and significantly shorter than those treated with rtPA (10 mg/kg).

LT3001 appears to have both thrombolytic and free radical scavenging effects with minimal risk of bleeding and potentially extended treatment time window. Therefore, LT3001 is being developed for the treatment of AIS.

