## 5.2.2 Clinical Studies

- [REDACTED], 4 clinical studies of LT3001 have been completed:
- LT3001-101, a first-in-human Phase I, single-ascending dose study conducted at 1 clinical site in the US, evaluating LT3001 [REDACTED]. The objectives of the study were to evaluate the safety, tolerability, and PK of single ascending doses [REDACTED] LT3001 drug product in healthy subjects. The results of this study were used to determine the doses to be assessed for a Phase I multiple-ascending dose study in healthy subjects, and to determine the Recommended Phase II Dose of LT3001 drug product to be tested in future studies in AIS patients, including this study.
  - LT3001-103, a randomized, double-blind, placebo-controlled, parallel-group study in healthy Chinese subjects to determine the safety, tolerability, and PK of multiple doses of LT3001 drug product [REDACTED]

- [REDACTED]. This study also determined the effect of multiple doses of LT3001 drug product on blood pressure and coagulation function.
- LT3001-105 was a two-part Phase I study of multiple doses of LT3001 drug product [REDACTED] in healthy adult subjects in the US. Part A was randomized, double-blind, placebo-controlled design to evaluate the safety, tolerability, and PK of multiple doses of LT3001 drug product. Part B was open-label without placebo-controlled design to assess the drug-drug interaction of LT3001 drug product when co-administered with aspirin, clopidogrel, apixaban or dabigatran.
  - LT3001-201, a Phase IIa, double-blind, single-dose, randomized, placebo-controlled study to evaluate the safety, tolerability, and potential efficacy of LT3001 drug product [REDACTED] in subjects with AIS.

In addition, 3 studies on LT3001 are planned/ongoing (enrollment stage):

- LT3001-202: Randomized, double-blind, placebo-controlled, parallel-group study to determine the safety and efficacy of multiple doses of LT3001 drug product [REDACTED] in patients with AIS.
- LT3001-203: Randomized, double-blinded, placebo-controlled Phase II study to evaluate the safety and efficacy of LT3001 drug product [REDACTED] in subjects with AIS undergoing endovascular thrombectomy.
- LT3001-205: current study described in this protocol.

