### 6.2 Study Endpoints

#### 6.2.1 Primary Endpoint

The proportion of subjects with AEs, judged to be probably or definitely related to the IP within 90 days after the 1st IP administration.

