SEVERE: An event that prevents normal everyday activities.

Table 4. Classification of Adverse Events by Relationship to Investigational Product

UNRELATED: This category applies to those AEs that are clearly and incontrovertibly due to extraneous causes (disease, environment, etc).
UNLIKELY: This category applies to those AEs that are judged to be unrelated to the IP but for which no extraneous cause may be found. An AE may be considered unlikely to be related to IP if or when it meets 2 of the following criteria: (1) it does not follow a reasonable temporal sequence from administration of the IP ; (2) it could readily have been produced by the subject's clinical state, environmental or toxic factors, or other modes of therapy administered to the subject; (3) it does not follow a known pattern of response to the IP; or (4) it does not reappear or worsen when the IP is readministered.
POSSIBLY: This category applies to those AEs for which a connection with the IP administration appears unlikely but cannot be ruled out with certainty. An AE may be considered possibly related if or when it meets 2 of the following criteria: (1) it follows a reasonable temporal sequence from administration of the IP; (2) it could not readily have been produced by the subject's clinical state, environmental or toxic factors, or other modes of therapy administered to the subject; or (3) it follows a known pattern of response to the IP.
PROBABLY: This category applies to those AEs that the investigator feels with a high degree of certainty are related to the IP. An AE may be considered probably related if or when it meets 3 of the following criteria: (1) it follows a reasonable temporal sequence from administration of the IP; (2) it could not be reasonably explained by the known characteristics of the subject's clinical state, environmental or toxic factors, or other modes of therapy administered to the subject; (3) it disappears or decreases on cessation or reduction in dose (note that there are exceptions when an AE does not disappear upon discontinuation of the IP, yet drug-relatedness clearly exists; for example, as in bone marrow depression, fixed drug eruptions, or tardive dyskinesia); or (4) it follows a known pattern of response to the IP.

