4.2.2. Exclusion Criteria

[figure not shown]
[figure not shown]
Individuals meeting any of the following criteria at Screening (Visit 1) or Baseline are ineligible to participate in this study:

This document is confidential.

1. During the current AIS episode, the subject has received or is scheduled to receive EVT and/or intravenous thrombolytic (e.g., recombinant tissue-type plasminogen activator) treatment based on the investigator's assessment of its potential benefit.
2. Subject has a pre-stroke disability (mRS >2).
3. Subject has Alberta Stroke Program Early CT Score of ≤5.
4. Subject has symptoms of suspected subarachnoid hemorrhage, even if CT is normal.
5. Subject has imaging evidence of acute intracranial hemorrhage, intracranial tumor (except meningioma without parenchymal mass effect), arteriovenous malformations, other central nervous system lesions that could increase the risk of bleeding, or aneurysm requiring treatment.
6. Subject has significant mass effect with midline shift.
7. Subject has pre-existing medical, neurological, or psychiatric disease that would confound the neurological or functional evaluations, e.g., seizures at onset of the current AIS, dementia.
8. Subject has current uncontrolled hypertension despite treatment: systolic blood pressure >185 mmHg or diastolic blood pressure >110 mmHg before dosing at Screening (Visit 1).
9. Subject has hemorrhagic diathesis, coagulation factor deficiency or recent oral anticoagulant therapy with International Normalized Ratio >1.7 or activated partial thromboplastin time >1.5 times of upper limit of normal range at Screening (Visit 1).
10. Subject has received conventional heparin within 48 hours before the 1st IP administration, except for low dose subcutaneous conventional heparin or low molecular weight heparin at a preventive dose.
11. Subject has received one of the new oral anticoagulants within 48 hours before the 1st IP administration, e.g., dabigatran, apixaban, rivaroxaban, and edoxaban, except for dabigatran-treated subject who has been given a reversal agent, idarucizumab, before the 1st IP administration.
12. Subject has platelet count <100,000/mm³ at Screening (Visit 1).
13. Subject has blood glucose concentration <50 mg/dL or >400 mg/dL at Screening (Visit 1).

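### Exclusion 10 bars only conventional heparin, so low molecular weight heparin above a preventive dose within 48 hours of first dosing is not excluded

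*Protocol*

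**What the plan says.** Exclusion 10 in Protocol 8.2 opens with "Subject has received conventional heparin within 48 hours before the" first dose of investigational product. It then carves out an exception: "except for low dose subcutaneous conventional heparin or low molecular weight heparin at a preventive dose". The synopsis has the same sentence, and SAP 4.2.2 repeats it, beginning "Subject has received conventional heparin within 48 hours before the 1st IP administration". No redaction falls inside any of the three copies.

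Protocol 9.5.1 refers the reader to 8.2 for restricted prior therapies and then states that the two excepted forms of heparin are permitted. It prohibits nothing itself in the visible text.

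The neighbouring Exclusion 11 is drafted without this problem for a different class: "Subject has received one of the new oral anticoagulants within 48 hours before the" first dose. It names apixaban and dabigatran among its examples and lets a dabigatran-treated patient in only after a reversal agent.

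**The concern.** An exception can only release cases that the main clause has caught. The main clause catches conventional heparin, and the sentence itself treats LMWH as a separate drug. The LMWH exception therefore does nothing, and LMWH above a preventive dose does not trigger the criterion.

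Two things are at stake.

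**Patient safety.** Protocol 5.2 says that LT3001 "is a novel small molecule designed to have both thrombolytic and free radical scavenging activities". The interaction work described in Protocol 5.2.1 and 5.2.2 covers aspirin, clopidogrel, apixaban and dabigatran; part B of the LT3001-105 study, for example, was run to "assess the drug-drug interaction of LT3001 drug product when co-administered with aspirin, clopidogrel, apixaban or dabigatran". No heparin is named in the visible text. The plan thus bars two anticoagulants for which it has interaction data (dabigatran unless reversed), while its literal wording admits LMWH above a preventive dose, for which it shows none. That ordering is unlikely to be intended.

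**Attribution of individual bleeds.** The primary endpoint counts only "AEs, judged to be probably or definitely related to the IP within 90 days" of the first dose. Table 4 in Protocol 12.7.1 asks, among its criteria, whether another treatment could explain the event. Recent LMWH above a preventive dose is such a treatment, and it makes a high relatedness grade harder to reach.

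This is not a claim of bias between arms. Eligibility is settled before central randomization, so such patients could fall in either group.

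**Working it through.** The plan gives no figure to reproduce. The check is a reading of the criterion, case by case, and a search for any other rule that would close the gap.

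**Step 1. Apply Exclusion 10 to each kind of heparin exposure within 48 hours before the first dose.** The reworded column adds LMWH to the main clause and leaves the exception alone.

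| Exposure | Caught by main clause as written? | Released by exception? | Excluded as written | Excluded as reworded |
|---|---|---|---|---|
| Conventional heparin other than low dose subcutaneous | yes | no | yes | yes |
| Low dose subcutaneous conventional heparin | yes | yes | no | no |
| LMWH at a preventive dose | no | nothing to release | no | no |
| LMWH above a preventive dose | no | nothing to release | **no** | **yes** |
| Total excluded | | | 1 of 4 | 2 of 4 |

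Deleting the LMWH half of the exception from the present text would change 0 of the 4 results, which confirms that it has no effect. The rewording changes 1 of 4, namely LMWH above a preventive dose.

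**Step 2. Look for another bar.**

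- Exclusion 9 concerns bleeding disorders, factor deficiency and recent oral anticoagulants, with INR and aPTT limits. LMWH is not named. Even if the aPTT limit is read on its own, it is a laboratory threshold and not a rule about exposure.
- Exclusion 11 covers the new oral anticoagulants only.
- Exclusion 23 leaves the matter to the investigator's discretion.
- Protocol 9.5.1 points back to 8.2 and adds a permission, not a prohibition. Some material near that section is not shown, so a restriction there cannot be ruled out, but Exclusion 10 itself would still read as it does.

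**Step 3. Follow a bleed through Table 4 when LMWH reasonably explains it.** Criterion (2), which requires that other therapy does not reasonably explain the event, is then unmet.

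- Definitely related: all 4 criteria are required. At most 4 − 1 = 3 can be met, so this grade is out of reach.
- Probably related: "An AE may be considered probably related if or when it meets 3 of the following criteria", of which there are 4. With criterion (2) unmet, 4 − 1 = 3 remain and every one of them must be met.

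A bleed that reaches neither grade is not counted in the primary endpoint.

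**The case against.** The strongest reply is that this is a slip of wording that sites will repair for themselves. An exception limited to the preventive dose has a purpose only if higher doses are barred, and 9.5.1 points the same way by singling out the preventive dose as permitted. Many sites would probably read it so, and nothing in the documents shows that any site read it otherwise. This stands as a limit on how often the gap would matter. It does not make the sentence correct: eligibility on a possible bleeding risk should not depend on each site mending the text, and under the literal wording enrolling such a patient breaches no criterion.

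A second reply is that the interaction results are reassuring. Protocol 5.2.1 reports no synergistic effect on clotting time in rats with dabigatran, clopidogrel or apixaban, and Protocol 5.3 reports a limited effect on coagulation in humans given apixaban or dabigatran. That tempers the likely seriousness, but none of it concerns LMWH, and the sponsor restricts apixaban and dabigatran despite those results.

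Third, the attribution argument is modest. In acute stroke the patient's own condition already competes as an explanation for many intracranial bleeds, and standard-of-care therapy is allowed after dosing. Symptomatic and asymptomatic intracranial hemorrhage are also recorded as secondary safety endpoints whose definitions need no relatedness judgment. This is fair: attribution is the lesser consequence, and its added effect cannot be sized.

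Finally, Protocol 14.7.1 classes as administrative only changes with no effect on subject safety. A change made for safety reasons may therefore need approval before use, so a memo to sites alone would understate the work. That point is accepted.

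**Conclusion.** The concern holds as a defect in the criterion as written. In all three copies Exclusion 10 leaves LMWH above a preventive dose unbarred, and no other visible rule bars it. The error affects one of the four exposure categories set out above; those categories describe the logic of the sentence and are not a measure of clinical impact. The number of patients concerned is unknown, and none is estimated. Sample size and planned analyses are unaffected.

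The conclusion rests on two premises: that LMWH is a different drug from conventional heparin, which the criterion's own wording supports, and that the sponsor meant to exclude higher-dose LMWH, which is inferred from the exception and from 9.5.1. Confidence is medium, because many sites may already apply the intended meaning and some text near 9.5.1 cannot be seen. The correction should be made, since the sentence decides who may receive a thrombolytic agent in a trial whose primary objective is safety.

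**What to change.** In Exclusion 10, insert *or low molecular weight heparin* directly after *conventional heparin* in the main clause and leave the exception as it is. Make the same change in the synopsis, Protocol 8.2 and SAP 4.2.2; the SAP copy only restates eligibility, so no analysis changes there. Treat departures from the corrected rule as protocol deviations, so that they reach the review under SAP 9.2 before database lock.

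The cost is one phrase in three places, a notice to sites, and most likely a protocol amendment with whatever approvals apply. No new procedure or data item is needed, because 9.5.1 already requires dose, regimen, route and dates for all treatments, including those begun before Screening. A few patients may become ineligible, but they are the ones the exception implies were to be kept out. If enrolment has already finished, the same medication records can be used to identify affected subjects before database lock.

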### **8.3 Study Withdrawal, Removal, and Replacement of Subjects**

If a subject discontinues study treatment and is withdrawn from the study for any reason, the study site must immediately notify the Medical Monitor (see contact details in [Section 12.7.3](#)). The date and the reason for study discontinuation must be recorded on the electronic case report form (eCRF). Subjects who discontinue early from the study will be asked to complete all assessments listed at Visit 6 as indicated in the Schedule of Assessments ([Table 1](#)).

In the event that a subject discontinues prematurely from the study because of a AE or serious AE, the AE or serious AE will be followed up until it resolves (returns to normal or baseline values) or stabilizes, or until it is judged by the Investigator to no longer be clinically significant.

Once a subject is withdrawn from the study, the subject may not reenter the study.

A subject may voluntarily withdraw or be withdrawn from the study at any time for reasons including, but not limited to, the following:

- unacceptable toxicity or AE

- subject withdrawal of consent: at any time, a subject's participation in the study may be terminated at his/her request or on the basis of the Investigator's clinical judgment. The reason for subject withdrawal will be noted on the eCRF.
- intercurrent illness: a condition, injury, or disease unrelated to the primary diagnosis that became apparent during treatment and necessitated the subject's termination from the study
- general or specific changes in the subject's condition that renders him/her ineligible for further treatment according to the inclusion/exclusion criteria
- subject fails to adhere to the protocol requirements (e.g., drug noncompliance, failure to make the return visits in the Follow-Up Period)
- lost to follow-up: the subject stopped coming for visits, and study personnel were unable to contact the subject 3 times
- pregnancy, as indicated in [Section 12.7.5](#).

Additionally, the Sponsor may stop the study at any time for safety, regulatory, legal, or other reasons aligned with good clinical practice (GCP). This study may be terminated at the discretion of the Sponsor or any regulatory agency. An Investigator may elect to discontinue or stop the study at his or her study site for any reason, including safety or low enrollment.

Randomized but not treated subjects will not be replaced.

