8.1. General Methods

- Analysis will be carried out using SAS® (version 9.4 or newer, SAS Institute Inc., Cary, NC). Templates for the summary tables, figures and subject data listings will be available separately.
- Data listings will include all data recorded for all enrolled and ITT subjects. Data will further be categorized by treatment group.
- Summary statistics will be presented by treatment group and overall (wherever applicable). For continuous variables, data will be summarized with the number of subjects (n), mean, standard deviation, median, minimum, and maximum by treatment group. For categorical variables, data will be tabulated with the number and proportion of subjects for each category by treatment group.
- This is an exploratory study, i.e., all statistical comparison between the treatment groups is not confirmatory but of descriptive nature. Where appropriate, descriptive statistics may be presented with 95% confidence intervals (CIs).
- The minimum and maximum will be reported with the same degree of precision (i.e., the same number of decimal places) as the recorded data. Measures of location (e.g., mean and median) will be reported to 1 degree of precision more than the recorded data, and measures of spread (e.g., standard deviation) will be reported to 2 degrees of precision more than the recorded data.
- The dictionary (MedDRA and WHO Drug) version used will be specified in corresponding data display footnote.
- Only data from protocol scheduled visits will be included in the summary tables. Data from unscheduled visits will not be included in summary tables but will be included in the listings.
- Any changes to the analyses that are not included in this SAP will be documented in the CSR.

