9.1. Subject Disposition and Withdrawals

All individuals who sign the ICF will be included in disposition summary. The number of subjects who are screened, screen failed with reasons, randomized, number of subjects in each analysis set, number of subjects who excluded from each analysis set (including reasons for exclusion), number of subjects who completed the study treatment, who discontinued the treatment with reasons for treatment discontinuation, number of subjects who discontinued the study treatment but remained in the study [REDACTED], number of subjects who completed the study [REDACTED], [REDACTED], who discontinued from the study with reasons for study discontinuation, death will be summarized by treatment group. All disposition data will be listed by subject and treatment group.

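### Protocol 8.3 does not separate stopping IP from leaving the study, which risks avoidable and possibly outcome-related loss of 90-day data

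*Protocol*

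**What the plan says.** Protocol 8.3 opens by treating stopping study treatment and being withdrawn from the study as one combined event. It then gives a single list at the level of the study: "A subject may voluntarily withdraw or be withdrawn from the study at any time for reasons including, but not limited to, the following". Three entries concern dosing rather than observation:

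- "subject fails to adhere to the protocol requirements (e.g., drug noncompliance, failure to make the return visits in the Follow-Up Period";
- unacceptable toxicity or an AE;
- "general or specific changes in the subject's condition that renders him/her ineligible for further treatment according to the inclusion/exclusion criteria".

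The exit is final: "Once a subject is withdrawn from the study, the subject may not reenter the study". On exit data, the section says: "Subjects who discontinue early from the study will be asked to complete all assessments listed at Visit 6". An AE that causes exit is followed until it resolves or stabilizes.

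Protocol 9.3.2 adds a second route. If the investigator becomes unblinded, the subject leaves the study unless there are ethical reasons against it, and the Medical Monitor must approve that exception. The same section reserves unblinding for managing an AE or another serious safety situation.

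SAP 9.1 plans to report the "number of subjects who discontinued the study treatment but remained in the study". No readable part of the protocol tells sites to keep such subjects in follow-up to Day 90.

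**The concern.** Reasons to stop giving a drug are not in themselves reasons to stop observing the patient. The synopsis puts dosing at six infusions in about 72 hours. The primary endpoint, mortality and recurrent stroke are counted to 90 days. A subject removed on Day 2 or 3 for a dosing-level reason could lose almost all of the outcome period, with no scientific gain.

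The loss may also be related to outcome. The second quoted entry re-applies the eligibility criteria after dosing has begun, and exclusion criterion 5 is imaging evidence of acute intracranial hemorrhage. A subject who bleeds between doses could be read as meeting it. Asymptomatic hemorrhage is not remote in this setting. In the earlier single-dose Phase IIa study (Protocol 5.3) it was seen within 7 days in 3 drug subjects (18.8%) and 1 placebo subject (12.5%), although these numbers are far too small to compare the arms. Unblinding is likewise tied to serious events. If such exits are commoner in one arm, or carry a different prognosis, the comparison of those who remain is distorted.

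**Working it through.** **1. Is there a planned figure to reproduce?** No. The sample-size text (Protocol 13.1, SAP 4.3) is not readable, so no planned event rate or dropout allowance is available. About 200 subjects at 1:1, or about 100 per arm, is readable. All rates below are assumptions.

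**2. Which analyses are exposed?**

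| Outcome | Handling of missing data | Source |
|---|---|---|
| Primary endpoint, mortality, other safety | No imputation | Protocol 13.4, SAP 11 |
| Recurrent stroke and other non-mRS/NIHSS efficacy | No imputation | SAP 10 |
| mRS and NIHSS proportion differences with CIs | Observed ITT data | SAP 10.1.1, 10.1.2 |
| mRS and NIHSS primary analysis approach | Multiple imputation, model redacted | SAP 10.1.3 |

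**3. What is still collected after exit?** The AE that caused exit is followed (Protocol 8.3). SAEs are reportable for 3 months after treatment stops (Protocol 12.7.3), which reaches about Day 90 because dosing is so short. Routine AE collection ends at the last follow-up visit (Protocol 12.7.1), so non-serious AEs that start after exit are lost.

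**4. Bias in an observed-data proportion.** Let p be the true responder rate, w the share removed and q the responder rate among those removed. Then:

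observed rate = (p − w·q) / (1 − w)

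Take no true effect, p = 0.40 for mRS 0-2 in both arms, and q = 0 (every removed subject is a non-responder).

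- 8% of drug and 3% of placebo removed: 0.40/0.92 − 0.40/0.97 = 0.435 − 0.412 = 2.2 points in favor of drug.
- 15% and 5% removed: 0.40/0.85 − 0.40/0.95 = 0.471 − 0.421 = 5.0 points.

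**5. Range, still with q = 0.**

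| Removed, drug v placebo | p = 0.30 | p = 0.40 | p = 0.50 |
|---|---|---|---|
| 10% v 5% | 1.8 | 2.3 | 2.9 |
| 15% v 5% | 3.7 | 5.0 | 6.2 |

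If removed subjects respond at half the arm's rate (q = p/2), each bias is p·(w/2)/(1 − w) per arm instead of p·w/(1 − w), exactly half. If removal and prognosis are the same in both arms, the bias in the difference is zero under no effect.

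**6. Undercount of 90-day events.** Assume a true 90-day risk of 10%, constant hazard, exit at Day 3, and no event seen after exit. The risk by Day 3 is 1 − 0.90^(3/90) = 0.35%. The observed risk is (1 − w)·10% + w·0.35%: 9.5%, 9.0% and 8.6% for w = 5%, 10% and 15%. For serious events this is an upper bound on the loss, because of the SAE reporting in step 3.

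**7. Scale.** At 100 per arm and p = 0.40, the standard error of a difference is √(2 × 0.40 × 0.60 / 100) = 0.069, about 7 points.

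**The case against.** The strongest reply is that 8.3 only permits withdrawal from the study, and that SAP 9.1 shows the trial expects some subjects to be off drug and still followed. The two texts can stand together. A reader might infer that these subjects must leave, or that the documents flatly contradict each other; neither follows from 8.3. What remains is that sites work from the protocol, which leaves the choice to discretion without an instruction to continue follow-up. Discretion over worsening subjects is how selective loss arises. Exit after unblinding is also the default rather than an option.

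A reader might also infer that exit assessments are analysed as Day 90 data, since early leavers do the Visit 6 assessments and SAP 8.1 says "Only data from protocol scheduled visits will be included in the summary tables". The documents do not show this. Protocol 8.3 fixes which assessments are done, not how they are labelled. The SAP 8.1 sentence keeps unscheduled data out of tables and relabels nothing. The schedule table, to which SAP 8.4 refers for visit windows, is not readable and may already settle the matter.

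Nor do the documents support saying that deaths after removal go uncounted. Death is an SAE and is reportable for about the whole 90 days. A death would be missed only if the site did not learn of it.

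Two further points stand. Noncompliance should be rare with supervised infusions in hospital, so the AE, ineligibility and unblinding routes matter more. The calculation in step 4 of the working describes observed-data differences, whereas the primary approach for mRS and NIHSS is multiple imputation. Whether that model copes with outcome-related exits cannot be judged from the redacted text.

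**Conclusion.** The point holds as a defect of wording with a real but unquantified risk. Protocol 8.3 and 9.3.2 allow, and after unblinding by default require, loss of follow-up for reasons that need only end dosing. No readable protocol text counters this. The exposed results are the safety endpoints, recurrent stroke and the observed-data mRS and NIHSS differences.

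The size rests wholly on assumed removal rates. In the worst case, with unequal removal and no responders among those removed, the observed mRS 0-2 difference moves by about 2 to 5 points at a true rate of 40%. It moves by half that if removed subjects respond at half the arm's rate. Against a standard error of about 7 points in an exploratory trial, this is a bias worth preventing. It does not support the stronger inference that the ITT analysis is invalid: the ITT population still contains everyone randomized.

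For the primary endpoint, the loss is confined mainly to non-serious AEs that start after exit and would have been judged probably or definitely related.

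**What to change.** In Protocol 8.3 and 9.3.2, separate discontinuation of IP from withdrawal from the study. State that any randomized subject who stops IP, for whatever reason and under the existing stopping rules, continues scheduled follow-up to Day 90 for mRS, AEs and vital status, unless consent for follow-up is withdrawn. Reconcile this wording with the disposition category in SAP 9.1.

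If the redacted visit windows do not already do so, add to SAP 8.4 that exit assessments are assigned by actual date and are not used as Day 90 data outside the Day 90 window.

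No change to when IP is stopped is proposed. The cost is a protocol amendment, with regulatory and ethics approval if it is classed as substantial under Protocol 14.7.1, a short SAP edit, and completion of already scheduled visits for what should be a few subjects.
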